# 3.2. Treatment Groups and Duration

This 12-week, Phase 3 study is a double-blind, vehicle-controlled treatment study in which subjects will be randomized in a 2:1 ratio to receive once daily treatment with either tapinar of cream, 1% or matching vehicle cream.

At the conclusion of the 12 weeks of treatment in this study, subjects will have the option to enroll in a separate Phase 3 open-label long-term safety and efficacy study of 40 weeks in duration. Details of that study are provided in a separate clinical trial protocol.

A subject will be considered to have completed this study when he/she completes all required procedures/visits for the 12-week double-blind treatment phase.

The end of study is defined as when the last active subject has completed the Week 16 Follow-up Visit 4 weeks after the end of treatment (if subject does not enroll in the separate long-term study) OR the last active subject has completed the 12 weeks of treatment in this study (if subject enrolls in the separate long-term study).

### 4. STUDY POPULATION

# 4.1. Type and Number of Subjects

Approximately 500 adult subjects with plaque psoriasis will be enrolled in the study at approximately 50 to 60 study sites in the US and Canada.

Protocol violations from inclusion and exclusion criteria are prohibited because ineligible study subjects can potentially jeopardize the scientific integrity of the study, regulatory acceptability, or subject safety. Therefore, adherence to the criteria as specified in the protocol is essential.

### 4.2. Inclusion Criteria

Each subject must meet all of the following criteria to be eligible to participate in the study:

- 1. Male and female subjects ages 18 to 75 years with clinical diagnosis of chronic plaque psoriasis and stable disease for at least 6 months prior to the study
- 2. Body surface area involvement  $\geq 3\%$  and  $\leq 20\%$  (the subject's scalp, palms, fingernails, toenails, and soles should be excluded from the %BSA calculations).
- 3. A PGA score of 2 (mild), 3 (moderate) or 4 (severe) at screening and baseline (pre-randomization). Subjects with mild and severe psoriasis will be limited to approximately 10% each of the total randomized population; the majority of the enrolled subjects (approximately 80%) will have a PGA of 3, signifying moderate disease.
- 4. Females of child-bearing potential and male subjects who are engaging in sexual activity that could lead to pregnancy must use at least 1 of the following adequate birth control methods while on study and for 4 weeks after the last exposure to study drug. Acceptable contraception methods are:
  - Male partner with vasectomy, OR
  - Male condom AND partner use of one of the contraceptive options below:
    - Spermicide
    - Contraceptive subdermal implant that meets effectiveness criteria including a < 1% rate of failure per year, as stated in the product label
    - Intrauterine device or intrauterine system that meets effectiveness criteria including a < 1% rate of failure per year, as stated in the product label

    - Oral contraceptive, either combined or progestogen alone
    - Injectable progestogen
    - Contraceptive vaginal ring
    - Percutaneous contraceptive patches

NOTE: Subjects using hormonal contraceptives must have been on a stable dose for at least 4 weeks before baseline.

These allowed methods of contraception are only effective when used consistently, correctly and in accordance with the product label. The Investigator is responsible for ensuring that subjects understand how to properly use these methods of contraception.

Non-child-bearing potential is defined as premenarchal or pre-menopausal females with a documented bilateral tubal ligation, bilateral oophorectomy (removal of the ovaries) or

**Tapinarof** 

hysterectomy, or hysteroscopic sterilization; or postmenopausal females defined as a cessation of menses for at least 12 months without an alternative medical cause. In questionable cases a blood sample with simultaneous follicle stimulating hormone (FSH) > 40 IU/mL is confirmatory. Documented verbal history from the subject is acceptable.

Subjects who are abstinent are eligible, but they must agree to use one of the birth control methods listed above if they start engaging in sexual activity that could lead to pregnancy during the study.

Female subjects of childbearing potential must have a negative serum pregnancy test at Screening and negative urine pregnancy test at Baseline (Day 1).

5. Capable of giving written informed consent, as applicable, which includes compliance with the requirements and restrictions listed in the informed consent form (ICF); written informed consent must be obtained prior to any study related procedures.

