#### 6.3.4. Clinical Safety Laboratory Assessments

All protocol-required laboratory assessments must be conducted in accordance with the Study Reference Manual or Laboratory Manual and the protocol Schedule of Assessments (Table 1). Laboratory requisition forms must be completed, and samples must be clearly labeled with the subject number, protocol number, site/center number, and visit date. Details for the preparation and shipment of samples will be provided by the laboratory and are detailed in the Study Reference Manual or the Laboratory Manual. Reference ranges for all safety parameters will be provided to the site by the laboratory responsible for the assessments.

A list of clinical laboratory tests and parameters is provided in Table 3.

All laboratory tests with values that are considered clinically significantly abnormal during participation in the study should be repeated until the values return to normal or baseline. If such values do not return to normal within a period judged reasonable by the Investigator, the etiology should be identified, if possible, and the Sponsor notified.

Clinical Study Flotocol - Ve

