#### **Table 3:** Laboratory Tests

Diagnostic Screening Tests				
HBsAg     Hepatitis C antibody	• Pregnancy tests: (serum at Screening and urine at other visits; women of CBP only)			
• Anti-HBc	• FSH (as needed in women of non-CBP only)			
That Tibe	• At the Investigator's discretion, subjects may be screen alcohol and illicit drug use.			
Serum Chemistry				
• BUN	• Total carbon dioxide	• Uric acid		
• Creatinine	• Calcium	• Total bilirubin (+fractionated		
• Glucose (fasting not required)	• AST	if required)		
• Sodium	• ALT	• Total protein		
• Potassium	Alkaline phosphatase	• Albumin		
• Chloride				
Hematology				
Platelet count	• RBC Indices:	• WBC Differential:		
• RBC count	• MCV	• Neutrophils		
• WBC count (absolute)	• MCH	• Lymphocytes		
Reticulocyte count	• MCHC	• Monocytes		
Hemoglobin	Reticulocyte percentage	• Eosinophils		
Hematocrit		• Basophils		
Urinalysis				
Specific gravity	• Dipstick: pH, Glucose,			
• Microscopic examination (if blood or protein is abnormal Protein, Blood Ketones				
ATT 1				

ALT = alanine aminotransferase; Anti-HBc = anti-hepatitis B core antigen; AST = aspartate aminotransferase; BUN = blood urea nitrogen; CBP = child-bearing potential; FSH = follicle-stimulating hormone; HBsAg = hepatitis B surface antigen; MCH = mean corpuscular hemoglobin; MCHC = mean corpuscular hemoglobin concentration; MCV = mean corpuscular volume; RBC = red blood cell(s); WBC = white blood cell(s).

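### The confirmatory FSH threshold is printed as > 40 IU/mL, which appears to be a unit misprint by a factor of 1,000, so the FSH test as written could confirm no one

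*Protocol*

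**What the plan says.** Inclusion criterion 4 defines non-child-bearing potential. It appears in the protocol synopsis and again in Section 4.2, and both places carry the same FSH sentence with the same unit: "In questionable cases a blood sample with simultaneous follicle stimulating hormone (FSH) > 40 IU/mL is confirmatory".

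The surrounding text matters for how far this reaches:

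- Just before it, the criterion lists surgical and sterilization routes that need no hormone test, and then "postmenopausal females defined as a cessation of menses for at least 12 months without an alternative medical cause".
- Just after it comes "Documented verbal history from the subject is acceptable".
- Table 3 in Section 6.3.4 lists the test as "FSH (as needed in women of non-CBP only", with no unit and no range.
- Section 6.3.4 also says "Reference ranges for all safety parameters will be provided to the site by the laboratory responsible for the assessments", so no FSH range is printed in the protocol.

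The SAP does not mention FSH.

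**The concern.** A threshold of 40 IU/mL is on a very different scale from 40 IU/L or 40 mIU/mL (these two are numerically the same). If serum FSH is reported in tens to low hundreds of IU/L, the printed threshold lies far above any result a laboratory would return. The sentence shows a second sign of faulty drafting: a blood sample with *simultaneous* FSH names no companion measurement, so words may be missing. Table 3 adds a third oddity, because it restricts the test to women already classed as not of child-bearing potential, although the test is meant to help settle that classification.

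The classification decides which women must have pregnancy tests (Table 1: screening, baseline, Weeks 4, 8, 12 and 16, and early termination) and which must use contraception if sexually active. Section 1.3.1.3 reports embryo-fetal findings in animals and names contraception and pregnancy testing as the mitigation. Section 4.1 prohibits departures from the eligibility criteria. A site that follows the text literally gets no use from the test. A site that compares the laboratory's number with 40 and ignores the unit is applying something other than the stated criterion.

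**Working it through.** The threshold is a stated criterion, not a derived figure, so there is no calculation in the plan to reproduce. The check is a unit conversion and a comparison.

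**Inputs**

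- Printed threshold: > 40 IU/mL (synopsis and Section 4.2).
- Conversions: 1 L = 1,000 mL; 1 IU = 1,000 mIU.
- Assumed postmenopausal serum FSH: 25 to 150 IU/L. The documents do not give this. It is an assumption about general scale only.

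**Step 1. Convert the printed threshold.**
40 IU/mL × 1,000 mL/L = 40,000 IU/L.
40 IU/mL × 1,000 mIU/IU = 40,000 mIU/mL.

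**Step 2. Compare with the same number on the smaller unit.**
40 mIU/mL = 40 IU/L, and 40,000 / 40 = 1,000. If mIU/mL or IU/L was meant, the printed threshold is exactly 1,000 times too large.

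**Step 3. Compare with the assumed range.**
25 to 150 IU/L is 0.025 to 0.15 IU/mL.
Upper end: 40,000 / 150 = 267.
Lower end: 40,000 / 25 = 1,600.
The printed cut-off is about 270 to 1,600 times the assumed values, so no woman in that range would exceed it.

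**Step 4. How much does the assumption matter?**
If true levels were 100 times the top of the assumed range, 100 × 150 = 15,000 IU/L, they would still be below 40,000 IU/L. The conclusion that the test cannot confirm anyone therefore does not depend on the exact endpoints. The multiples in Step 3 do.

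**Step 5. Is there anything in the documents that corrects the unit?**
No. The synopsis and Section 4.2 agree with each other, which makes a text-extraction error unlikely. Table 3 gives no unit, and Section 6.3.4 leaves ranges to the laboratory. The documents do not contradict themselves on the unit. The inference of a misprint comes from the general scale of serum FSH.

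**Step 6. What happens to a woman the test does not confirm?**
She may still qualify as of non-child-bearing potential by 12 months without menses, by documented verbal history, or by surgical or sterilization history. Otherwise she is handled as of child-bearing potential. That status is not among the exclusion criteria in Section 4.3. She needs negative pregnancy tests at screening and baseline, and one of the listed contraceptive methods if she engages in sexual activity that could lead to pregnancy. Section 4.2 states that abstinent subjects are eligible.

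**The case against.** A reader might infer that no woman in a questionable case can be shown to be of non-child-bearing potential. The documents do not support that. The sentence right after the FSH line accepts documented verbal history, and FSH is described as confirmatory, not as required. One can debate whether the verbal-history sentence covers the questionable cases or only the surgical and menstrual history, but it cannot be ignored. What the text supports is narrower: the FSH test, as printed, cannot do the confirming.

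A reader might also infer that women would be screened out, or that fetal safety is at risk. Neither follows. Exclusion would arise only if a woman were sexually active and declined every listed method. Literal use leads to more contraception and more pregnancy testing, so it errs on the side of precaution.

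Three further objections have weight. The misprint is inferred from outside the documents, so certainty attaches only to the printed text and the conversion. FSH is measured only as needed, and the number of questionable cases is not given and could be zero, so inconsistency across the 50 to 60 sites is possible but not shown. No statistical quantity in the protocol or SAP depends on the unit.

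These objections limit the consequence and leave the defect in place. The protocol offers a laboratory test for doubtful cases and sets its decision threshold at a level the test would not reach.

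**Conclusion.** The point holds in limited form. The threshold is printed as 40 IU/mL in two places and equals 40,000 IU/L. Given only that postmenopausal serum FSH is nowhere near that level (assumed here as 25 to 150 IU/L), the test as printed confirms no one, and the unit appears to be wrong by a factor of 1,000. The printed text and the factor are certain; the diagnosis of a misprint is a strong inference.

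The effect is an unusable confirmatory test, unnecessary precautions for some women if the text is followed literally, and possible differences between sites if it is not. How many women are affected cannot be worked out from the documents. There is no effect on sample size, endpoints, error rates or analyses. It still merits correction, because it is a decision threshold inside an eligibility criterion that Section 4.1 says must be followed as specified.

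**What to change.** The sponsor should:

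1. Verify the FSH unit against the unit in which the study laboratory reports the test, and confirm the intended cut-off. This review does not set that cut-off.
2. Correct the synopsis and Section 4.2 together, so that they stay identical.
3. Print the same unit beside FSH in Table 3, and reword the entry so that it covers women whose status is being established.
4. Delete *simultaneous*, or name the measurement that it refers to.
5. Say whether documented verbal history is enough in a questionable case, so that its relation to the FSH result is clear.

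The cost is a short text correction in two places plus the Table 3 entry, by amendment or clarification letter. It needs no new test, no extra subjects and no change to the SAP.

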## 4.3. Exclusion Criteria

A subject who meets any of the following criteria will be excluded and considered ineligible for participation in the study:

- 1. Psoriasis other than plaque variant
- 2. Any sign of infection of any of the psoriatic lesions
- 3. Concurrent conditions or history of other diseases:
- a. Immunocompromised (eg, lymphoma, acquired immunodeficiency syndrome) or medical history of positive human immunodeficiency virus (HIV) antibody at Screening
- b. Chronic or acute systemic infection requiring treatment with systemic antibiotics, antivirals, antiparasitics, antiprotozoals, or antifungals within 4 weeks prior to the Baseline visit
- c. Acute active bacterial, fungal, or viral (herpes simplex, herpes zoster, chicken pox) skin infection within 1 week prior to the Baseline visit
- d. Significant dermatologic or inflammatory condition other than plaque psoriasis that, in the Investigator's opinion, would make it difficult to interpret data or assessments during the study
- 4. Screening alanine aminotransferase (ALT) or aspartate aminotransferase (AST)  $\geq$  1.5x the upper limit of normal (ULN)
- 5. Screening total bilirubin > 1.5 x ULN; total bilirubin > ULN and  $\leq 1.5$  x ULN is acceptable if bilirubin is fractionated and direct bilirubin  $\leq 35\%$ .
- 6. Corrected QT (QTcF) interval > 475 msec.
- 7. Current or chronic history of liver disease, known hepatic or biliary abnormalities (with the exception of Gilbert's syndrome or asymptomatic gallstones), presence of hepatitis B surface antigen (HBsAg), or positive hepatitis C antibody test result, or a positive antihepatitis B core antigen (anti-HBc) result. Subjects with a history of HCV infection who were medically cured and have an undetectable viral load are eligible to enroll. Subjects with a history of stable non-alcoholic fatty liver disease without evidence of active inflammation (elevated ALT/AST ≥ 1.5x ULN) or cirrhosis are eligible to enroll.
- 8. Ultraviolet (UV) light therapy or prolonged exposure to natural or artificial sources of UV radiation (eg, phototherapy, tanning beds/booths, or therapeutic sunbathing) within

- 4 weeks prior to the Baseline visit and/or plans to have such exposures during the study which could potentially impact the subject's psoriasis (as determined by the Investigator).
- 9. Use of any prohibited medication within the indicated period before the Baseline visit. NOTE: Prohibited concomitant medications, therapy, etc., during the defined period are as listed in the bullets below. If a subject requires any of these medications throughout the study period, he/she may be excluded from or discontinued from the study.
  - Minimum of 5 half-lives for biologic agents: eg, 12 months for rituximab; 8 months for ustekinumab; 5 months for secukinumab; 12 weeks for golimumab; 10 weeks for ixekizumab; 8 weeks for infliximab, adalimumab, or alefacept; and 4 weeks for etanercept.
  - 4 weeks for systemic treatments: cyclosporin, interferon, methotrexate, apremilast, tofacitinib, mycophenolate, thioguanine, hydroxyurea, sirolimus, azathioprine, other systemic immunosuppressive or immunomodulating agents, fumaric acid derivatives, vitamin D3 and analogs (> 5000 IU/day), retinoids (eg, acitretin, isotretinoin), psolarens, corticosteroids, or adrenocorticotropic hormone analogs.
  - 2 weeks for immunizations with a live viral component; drugs known to possibly worsen psoriasis, such as beta-blockers (eg, propranolol), lithium, iodides, angiotensin-converting enzyme inhibitors, and indomethacin, unless on a stable dose for > 12 weeks.
  - With the exception of non-medicated emollients, 2 weeks for topical treatments including corticosteroids, antihistamines, immunomodulators, anthralin (dithranol), Vitamin D derivatives (eg, calcipotriene, calcipotriol), retinoids (Note: 4 weeks for tazarotene), or coal tar.
- 10. A history of or ongoing serious illness or medical, physical, or psychiatric condition(s) that, in the Investigator's opinion, may interfere with the subject's participation in the study and ability to understand and give informed consent.
- 11. Pregnant females as determined by positive serum (screening) or urine (baseline) human chorionic gonadotropin test at screening or prior to dosing.
- 12. Lactating females
- 13. History of sensitivity to the study drugs, or components thereof or a history of drug or other allergy that, in the opinion of the Investigator or Medical Monitor, contraindicates the subject's participation in the study.
- 14. The subject has received an investigational product within the following time period prior to the first dosing day in the current study: 30 days, 5 half-lives, or twice the duration of the biological effect of the study drug (whichever is longer).
- 15. Current or a history of cancer within 5 years except for adequately treated skin basal cell carcinoma, squamous cell carcinoma or carcinoma in situ of the cervix (surgical excision or electrodessication and curettage).
- 16. Subjects with active systemic infection that required oral, intramuscular, or intravenous administration of antibiotics, antifungal or antiviral agents within 4 weeks of Baseline/Day 1.
- 17. Concurrent skin lesions in the treatment area that, in the opinion of the Investigator, would either interfere with study evaluations or affect the safety of the subject.

- 18. Subjects with advanced disease or abnormal laboratory test values that could affect the safety of the subject or the implementation of this study.
- 19. Previous known participation in a clinical study with tapinarof.
- 20. Evidence of significant hepatic, renal, respiratory, endocrine, hematologic, neurologic, psychiatric, or CV system abnormalities or laboratory abnormality that will affect the health of the subject or interfere with interpretation of the results.

# 4.4. Lifestyle Restrictions

Subjects must avoid UV light, phototherapy, and excessive sun exposure throughout the study. When prolonged exposure cannot be avoided, use of sunscreen products (except on psoriasis plaques) and protective apparel are recommended.

# 4.5. Screening/Baseline Failures

To determine subject eligibility at Screening and Baseline, a single repeat of tests or procedures may be allowed at the discretion of the Investigator; the Medical Monitor should be consulted if needed.

Screen failures are defined as subjects who consent to participate in the clinical study but are not subsequently randomized. A minimal set of screen failure information is required to ensure transparent reporting of screen failure subjects to meet the Consolidated Standards of Reporting Trials publishing requirements and to respond to queries from regulatory authorities. Minimal information includes demography, screen failure details, eligibility criteria, and any SAEs.

### 4.6. Withdrawal Criteria

A subject may voluntarily discontinue treatment and/or withdraw from participation in this study at any time at his/her own request, or may be discontinued from study treatment at any time at the discretion of the Investigator for safety, behavioral, compliance, or administrative reasons. Subjects withdrawn from the study will not be replaced.

### 4.6.1. Reasons for Withdrawal from the Study

Study drug will be discontinued for any of the following reasons:

- Subject has an AE that is considered to be related to study drug or procedures AND is severe enough to warrant treatment discontinuation, as determined by the Investigator (Section 8.1).
- Subject requires concurrent prohibited medication during the study. If, in the opinion of the Investigator and the study Medical Monitor, such medication will not interfere with the conduct or interpretation of the study or compromise the safety of the subject, then the subject may continue to receive study drug. If the subject is discontinued from study drug, they may remain in the study for safety assessments as needed, at the discretion of the Investigator and Medical Monitor.
- Pregnancy
- Any Grade 3 or 4 AE considered causally related to study drug (Section 8.2.2)

Study drug may be discontinued for any of the following reasons:

• Subject noncompliance

- Investigator noncompliance
- Discontinuation of the study at the request of the Sponsor, regulatory agency, or an Institutional Review Board (IRB)/Independent Ethics Committee (IEC).

If a subject meets a withdrawal criterion during treatment, an Early Termination visit will be required (Section 7.5).

#### 4.6.2. Withdrawal Procedures

The primary reason for the discontinuation of study drug and/or withdrawal from study must be recorded in the source document and on the electronic case report form (eCRF). If a subject is prematurely discontinued from study drug(s), the Investigator must make every effort to perform an Early Termination Visit (Section 7.5) and document the primary reason for withdrawal.

Should a subject fail to attend a required study visit, the site should attempt to contact the subject and reschedule the missed visit as soon as possible. The site should also counsel the subject on the importance of maintaining the assigned visit schedule and ascertain whether the subject wishes to and/or should continue in the study based on previous noncompliance. In cases where the subject does not return for the rescheduled visit or cannot be reached to reschedule the missed visit, the site should make every effort to regain contact with the subject so that they can appropriately be withdrawn from the study with a primary reason of "Lost to Follow-up".

